### **Severe hyperkalemia**

Severe hyperkalemia will be defined as  $S\text{-}K > 6.5 \text{ mmol/L}$  (yes/no) after the LIDI. The same analysis as for the classification of potassium into normal / abnormal (i.e. a logistic regression) will be performed.

### **Sensitivity Analysis**

To assess sensitivity of the result to missing data assumptions, binary endpoints based on potassium levels at the 12 months will be analysed using Full Analysis Set (all randomized subjects). Subjects with missing values will be considered as non-responders. For severe hyperkalemia endpoint ( $S\text{-}K > 6.5 \text{ mmol/L}$  (yes/no)), subjects with missing values will be considered as having severe hyperkalemia.

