### 9.2 Sample Size Determination

The study is event-driven. The primary objective of the study is to evaluate the efficacy of SZC versus placebo in reducing the incidence of the primary composite endpoint. Assuming the true HR for SZC versus placebo is 0.8, 730 primary endpoint events will result in approximately 85% power to demonstrate a statistically significant difference at either interim analysis (two-sided significance level of 1.64%) or at final analysis (two-sided significance level of 4.46%). Based on an assumption that the event rate of the primary composite endpoint is approximately 11 per patient-year in the placebo group, it is expected that approximately

2800 participants will need to be randomized. The anticipated recruitment period is planned to be 32 months. The anticipated average treatment period is approximately 37 months, which in practice will be dependent on the actual event rate observed during the study, as the study duration is event-driven. Any decision to increase or decrease participant numbers or extend or shorten study duration will be based on blinded event rate data.

Assuming a screen failure rate of 50%, approximately 5600 participants will be enrolled to achieve approximately 2800 participants randomly assigned (1:1) to study intervention (SZC or placebo).

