## **3 DATA ANALYSIS CONSIDERATIONS**

### **3.1 Timing of Analyses**

The study involves two interim analyses (the first interim analysis is for futility and the second interim analysis is for efficacy) and the final analysis.

Thus, there are three timepoints for planned analyses in the study: one corresponding to study completion, planned to take place when 730 subjects had an adjudicated primary composite event, and the other two corresponding to interim analyses planned to take place when 292 (40% information fraction) and 511 (70% information fraction) subjects, respectively had an adjudicated primary composite event. The interim analyses will be conducted by independent data monitoring committee (DMC) and will mainly be aimed at evaluating the primary objective of the study with the possibility of early stopping for either futility (at n=292 events) and for efficacy (at n=511 events). In case of an early stopping of the study at efficacy interim analyses, all analyses as specified in this document will be conducted. However, if the study stops for futility, only selected analyses covering key efficacy and safety outcomes will be conducted.

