### **3.3 Sample Size Determination**

The study is event-driven. The primary objective of the study is to evaluate the efficacy of SZC versus placebo in reducing the incidence of the primary composite endpoint.

Assuming the true HR for SZC versus placebo is 0.8, 730 primary endpoint events will result in 84.7% statistical power to demonstrate a statistically significant difference at either second interim analysis using two-sided significance level of 1.64% or at the final analysis using two-sided significance level of 4.46%. Based on an assumption that the event rate of the primary composite endpoint is approximately 0.11 per patient-year in the placebo group, it is expected that approximately 2800 participants will need to be randomized. The anticipated recruitment period is planned to be 32 months. The anticipated average treatment period is approximately 37 months, which in practice will be dependent on the actual event rate observed during the study, as the study duration is event driven. Any decision to increase or decrease participant numbers will be based on blinded event rate data (e.g., observed overall event rate), and study discontinuation rate.

Assuming a screen failure rate of 50%, approximately 5600 participants will be enrolled to achieve approximately 2800 participants randomly assigned (1:1) to study intervention (SZC or placebo).

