#### **4.2.3 Multiplicity/Multiple Comparisons**

Testing for efficacy will be performed at two time points, first at 0.7 information fraction and at the final analysis. The significance levels for the interim and the final analyses will be adjusted to control the overall type I error rate at two-sided 5%. At the efficacy interim analysis, the hypothesis for the primary endpoint will be tested at two-sided 1.64% significance level (O'Brian and Fleming method implemented by East 6.5, Copyright © 2018 Cytel Inc.). If the outcome of the interim analysis is to stop the trial for efficacy, then the interim analysis results will be considered as the primary efficacy results. However, a supplementary analysis will be performed with the additional data up to the study termination.

If the trial does not stop at any interim, then the final analysis planned at 730 adjudicated events, will be performed at a two-sided significance level of 4.46%. If the actual information fraction at the efficacy interim look deviates from 0.70, the significance level

for the final analysis will be adjusted based on the actual number of adjudicated primary events at the interim and final analyses.

To control the familywise Type I error rate, a fixed sequence multiple testing procedure for primary and secondary endpoints will be performed.

For the primary endpoint, the following hypothesis will be tested:

$H_0: HR[\text{SZC:placebo}] = 1$

Versus

$H_1: HR[\text{SZC:placebo}] \neq 1$

If study is terminated early prior to conducting efficacy and futility interim analyses and for reasons unrelated to efficacy, primary endpoint will be tested at 5% two-sided significance level.

Once the null hypothesis concerning the primary efficacy endpoint is rejected, the hypotheses for the secondary efficacy endpoints will be tested separately in the order listed in Table 2, with the same alpha level as the primary endpoint. The testing procedure will continue down the hierarchy if the current endpoint is rejected and will stop if the current endpoint is not rejected.

No multiplicity correction will be applied to the family of exploratory analyses. Hence, the results obtained from these should be regarded as hypothesis generating, rather than confirmatory.

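### After an early stop, the 12-month potassium sensitivity analysis would score participants whose visit was not yet due as failures

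*SAP*

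**What the plan says.** Three endpoints are read at a single visit, Visit 8 (Day 365 ± 7, Protocol Table 2): S-K 4.0-5.5 mmol/L (first in the secondary testing order of SAP Table 2), S-K > 6.5 mmol/L (fifth), and S-K 4.0-5.0 mmol/L (exploratory).

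SAP 4.2.2 bases the main analysis on available values, without imputation. Its Sensitivity Analysis then takes the whole Full Analysis Set. For the normokalemia endpoints, "Subjects with missing values will be considered as non-responders"; for severe hyperkalemia, "subjects with missing values will be considered as having severe hyperkalemia".

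The SAP foresees three early endings:

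- **Efficacy, 511 events (SAP 3.1):** in that case "all analyses as specified in this document will be conducted".
- **Futility, 292 events (SAP 3.1):** only a selection of key efficacy and safety analyses is promised.
- **Before the interims (SAP 4.2.3):** "If study is terminated early prior to conducting efficacy and futility interim analyses and for reasons unrelated to efficacy", the primary endpoint is tested at two-sided 5%.

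SAP 3.4.1.1 lets the study end date (SED) follow an early-stopping decision, and SAP 3.4.2 applies no visit windows. Neither document separates a visit that was missed from one that had not yet come due. SAP 4.2.4 says that missing data will not be imputed for secondary or exploratory endpoints.

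**The concern.** The endpoints have a fixed time point, but the analyses are triggered by event counts or by a decision to stop. If the study ends while recruitment is running, or less than a year after it closes, some participants cannot have a Visit 8 value. Read literally, the sensitivity rule counts a participant randomised one month before the cut-off as having S-K > 6.5 at month 12.

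The SAP does not treat the primary endpoint this way. SAP 4.2.1.3 regards censoring as premature only when its cause is something other than the SED, and Appendix 2 imputes no further than the SED. For the potassium endpoints that distinction is absent.

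At stake is the only imputation-based check the SAP gives these endpoints. It is meant to probe assumptions about missing data, and visits that were never due say nothing about those assumptions. The check would report a severe-hyperkalemia rate in each arm that depends partly on recruitment dates, and odds ratios shrunk toward 1.

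**Working it through.** **Inputs.** From the documents: 2800 randomised 1:1; "The anticipated recruitment period is planned to be 32 months" (Protocol 9.2); "The anticipated average treatment period is approximately 37 months", an event rate of "approximately 0.11 per patient-year in the placebo group", and "Assuming the true HR for SZC versus placebo is 0.8" (SAP 3.3); looks at 292, 511 and 730 events (SAP 3.1). Protocol 9.2 prints the rate as 11 per patient-year; only the SAP's 0.11 is usable. My assumptions: uniform entry, exponential event times, and no attrition in the base case. The documents give no dropout or 12-month S-K rates.

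**Step 1: reproduce the plan's timeline.** The monthly rates are λ = 0.11/12 = 0.00917 (placebo) and 0.088/12 = 0.00733 (SZC). Expected events at calendar month T, summed over the two arms:

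- T ≥ 32: 1400 × Σ{1 − [exp(−λ(T−32)) − exp(−λT)]/(32λ)}
- T < 32: 1400 × (T/32) × Σ{1 − [1 − exp(−λT)]/(λT)}

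At T = 53 this is 1400 × (0.2851 + 0.2359) = 729, against 730 planned. Average follow-up is 53 − 16 = 37 months, which matches the plan.

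**Step 2: date the interim looks.** At T = 29.6: 1295 × (0.1242 + 0.1011) ≈ 292. At T = 40.8: 1400 × (0.2005 + 0.1644) ≈ 511.

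**Step 3: share short of month 12.** Entry runs at 2800/32 = 87.5 a month, so 12 months of recruits is 1050. The share is 12/T up to month 32 (for T above 12), (44 − T)/32 from month 32 to 44, and 0 after that.

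| Point | Month | Randomised | Not yet due | Share |
|---|---|---|---|---|
| Stop before the looks (example) | 24 | 2100 | 1050 | 50% |
| 292 events | 29.6 | 2591 | 1050 | 40.5% |
| Recruitment closes | 32 | 2800 | 1050 | 37.5% |
| 511 events | 40.8 | 2800 | 279 | 10% |
| 730 events | 53.0 | 2800 | 0 | 0% |

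Range when the assumptions change:

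- Attrition of 5-15% a year: 38-40% at 292 events, 0-5% at 511.
- Placebo rate 0.07 to 0.13: 21-44% at 292, 0-22% at 511.
- HR 1: 43% and 18%.
- Three more months of follow-up before the cut-off: at 292 events with recruitment stopped at the look, (29.6 − 20.6)/29.6 = 30%; at 511 events, (44 − 43.8)/32, under 1%.

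**Step 4: dilution.** With not-due share m and true proportion p, the check reports m + (1 − m)p for S-K > 6.5 and (1 − m)p for normokalemia. The true proportions below are illustrative assumptions.

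| Endpoint (placebo v SZC) | m | Reported | Odds ratio, true → reported |
|---|---|---|---|
| S-K > 6.5 (10% v 3%) | 10% | 19.0% v 12.7% | 0.28 → 0.62 |
| S-K > 6.5 (10% v 3%) | 40% | 46.0% v 41.8% | 0.28 → 0.84 |
| S-K 4.0-5.5 (35% v 55%) | 40% | 21.0% v 33.0% | 2.27 → 1.85 |

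On the log scale the loss at m = 40% is 1 − ln 0.84/ln 0.28, about 87%, for S-K > 6.5, but only about 25% for normokalemia. With assumed rates of 15% v 5% and m = 41%, the severe-hyperkalemia odds ratio moves from 0.30 to 0.79, a loss of about 80%.

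**Step 5: would significance go?** Using SE² = the sum of reciprocal cell counts, with no other missing values:

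- S-K > 6.5, m = 10%, 1400 per arm: 0.62 (95% CI 0.50-0.76), p < 0.0001.
- S-K > 6.5, m = 40%, 1295 per arm: 0.84 (0.72-0.98), p ≈ 0.03.
- S-K 4.0-5.5, m = 40%, 1295 per arm: 1.85 (1.55-2.21), p < 0.0001.
- S-K > 6.5, m = 50%, 1050 per arm: p ≈ 0.11.

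**The case against.** Much can be said for leaving the rule alone.

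- **Confirmatory tests.** A reader might infer that the secondary hierarchy is at risk. The documents do not support that: SAP 4.2.2 runs those tests on available values, so participants not yet due drop out.
- **Size.** A reader might attach the 40% to every early stop. It belongs to a stop near or before the 292-event look. After a futility stop SAP 3.1 promises only selected analyses, so the check may never be run. The one early stop for which the full set is expressly required is the efficacy stop, where the share is about 10% or less on the planning figures. For termination before the interims, SAP 4.2.3 sets the primary test level but does not say whether sensitivity analyses follow. The hierarchy would open only if the primary succeeded with fewer than 292 events; at HR 0.8 and two-sided 5%, power at 292 events is about 48%.
- **Robustness.** A reader might infer that a real potassium effect would look fragile. At 10% or 40% not due, each illustrated odds ratio keeps its direction and p < 0.05; only S-K > 6.5 at 50% not due loses significance.
- **Direction and context.** Not-yet-due participants should be balanced by arm, so the rule cannot create a false benefit. SAP 4.5.2.2 also tabulates S-K > 6.5 among those with a Visit 8 value, so the observed rates stand beside the worst-case ones.

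All of this stands and limits the scope. It does not answer the literal problem: the rule as written gives a misleading check after an early stop, and nothing else in the SAP corrects it.

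**Conclusion.** The point holds as a defect in one sensitivity rule that matters only after an early stop. The not-due share is 0% at the planned 730-event analysis, about 0-10% at an efficacy stop, and about 40% or more for a termination before the 292-event look. These figures rest on uniform entry and the SAP's planning rates. A placebo rate of 0.13 would raise the efficacy-stop share to 22%, a rate of 0.07 would lower the share at 292 events to 21%, and a delay between the decision and the cut-off lowers both.

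The consequence is attenuation of the check's odds ratios and, for S-K > 6.5, an inflated reported rate in both arms. It is concentrated in that endpoint, where even 10% not due moves an assumed 0.28 to 0.62. The exact sizes depend on S-K rates that the documents do not give. No confirmatory conclusion changes. The correction is worth making because it is cheap and brings the rule into line with how the SAP treats administrative censoring for the primary endpoint.

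**What to change.** In the Sensitivity Analysis of SAP 4.2.2:

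1. Analyse all randomised participants who either have an observed Visit 8 S-K value or whose Visit 8 window (Day 365 + 7) closed on or before the SED, or the data cut-off after an early stop.
2. Apply the non-responder or severe-hyperkalemia coding only to those who were due but have no value. Due status counts from randomisation, so participants who died or withdrew before a visit that would have been due stay in.
3. Report participants not yet due as a separate count by arm.

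The observed-value clause matters. A rule based on Day 372 alone would discard valid samples taken from Day 358 onward when Day 372 falls after the cut-off, although the main analysis keeps them.

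In the same edit, reconcile this section with SAP 4.2.4, which excludes imputation for secondary and exploratory endpoints while SAP 4.2.2 assigns failures to missing values.

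Cost: a short SAP wording change and one date condition in the program, with no new data or participants. On the planning figures the 730-event result does not change. The downside is a smaller denominator after an early stop: on those figures 2800 − 279 = 2521 at 511 events, and 2591 − 1050 = 1541 at 292 events.

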### **Supplementary analyses**

The distribution of the SK values at the 12 months visit, as well as at baseline, in each treatment arm, will be illustrated by means of a box plot. A complimentary table presenting the summary statistics (mean, SD, median, min, max, quartiles) describing the distribution of SK, as well as the distribution of difference in SK as compared to baseline, per treatment arm, will also be provided.

#### **4.2.2.1 Time to first event analyses**

In addition to the main analysis of the composite primary endpoint, and its components, the difference between the two treatment arms in time to the following events (in days) will be analyzed:

- Time to first instance of use of rescue therapy for hyperkalemia
- Time to CV death
- Time to death from any cause
- Time to first occurrence of SCD, stroke, or hospitalization/intervention/ED visit due to arrhythmias (AF, bradycardia, asystole, VT), or use of rescue therapy (exploratory objective)

For all of these endpoints, the analysis described in Section 4.2.1.4 (i.e. the main analysis of the primary objective) will be replicated, with the censoring rules given in Table 2 and Table 3. KM estimates of the CDF in the respective treatment arms will be plotted as a supportive illustration.

### **Sensitivity analyses**

A sensitivity analysis of the analysis of time to CV death, where deaths adjudicated as ‘undetermined’ cause are included as endpoint events, instead of being treated as censoring

events, will be performed using the same approach as for the main analysis of time to CV death. No plots of KM estimates will be produced.

#### **4.2.2.2 Number of events analyses**

Two analyses aimed at examining the difference in the expected number of events of interest, per a unit of time, between treatment arms will be performed. In the first analysis, aimed at evaluating the corresponding secondary objective, the events of interest are hospitalizations /interventions /ED visits due to arrhythmias. Only arrhythmias events that are positively adjudicated will be considered. Multiple hospitalizations /interventions /ED visits due to a single positively adjudicated arrhythmias will be counted as one event. In the second analysis, aimed at evaluating the corresponding exploratory objective, the events of interest are use of rescue therapy for hyperkalemia.

For both of these endpoints, a negative binomial regression model with number of events as response and the same covariates as in the main analysis of the primary endpoint (Section 4.2.1.4) will be used. The logarithm of the subject's corresponding follow-up time will be used as an offset variable in the model to adjust for subjects having different follow-up times during which the events can occur. See Table 2 and 3 for the definition of the follow-up time (censoring).

The estimated event rate in the respective treatment arm, rate ratio between these, corresponding 95% confidence interval, and two-sided p-value will be presented. Total number of events that occurred up to the point of censoring will also be presented, by treatment group.

Time to event analysis for recurrent events may be conducted as a supplementary analysis.

#### **4.2.3 Multiplicity/Multiple Comparisons**

Testing for efficacy will be performed at two time points, first at 0.7 information fraction and at the final analysis. The significance levels for the interim and the final analyses will be adjusted to control the overall type I error rate at two-sided 5%. At the efficacy interim analysis, the hypothesis for the primary endpoint will be tested at two-sided 1.64% significance level (O'Brian and Fleming method implemented by East 6.5, Copyright © 2018 Cytel Inc.). If the outcome of the interim analysis is to stop the trial for efficacy, then the interim analysis results will be considered as the primary efficacy results. However, a supplementary analysis will be performed with the additional data up to the study termination.

If the trial does not stop at any interim, then the final analysis planned at 730 adjudicated events, will be performed at a two-sided significance level of 4.46%. If the actual information fraction at the efficacy interim look deviates from 0.70, the significance level

for the final analysis will be adjusted based on the actual number of adjudicated primary events at the interim and final analyses.

To control the familywise Type I error rate, a fixed sequence multiple testing procedure for primary and secondary endpoints will be performed.

For the primary endpoint, the following hypothesis will be tested:

$H_0: HR[\text{SZC:placebo}] = 1$

Versus

$H_1: HR[\text{SZC:placebo}] \neq 1$

If study is terminated early prior to conducting efficacy and futility interim analyses and for reasons unrelated to efficacy, primary endpoint will be tested at 5% two-sided significance level.

Once the null hypothesis concerning the primary efficacy endpoint is rejected, the hypotheses for the secondary efficacy endpoints will be tested separately in the order listed in Table 2, with the same alpha level as the primary endpoint. The testing procedure will continue down the hierarchy if the current endpoint is rejected and will stop if the current endpoint is not rejected.

No multiplicity correction will be applied to the family of exploratory analyses. Hence, the results obtained from these should be regarded as hypothesis generating, rather than confirmatory.

#### **4.2.4 Handling of Dropouts and Missing Data**

Missing data imputation will not be adopted for secondary, or exploratory endpoints and no supplementary analyses of the same type as the tipping point analysis described in Section 4.2.1.3 will be performed.

The missing data will also be described in terms of the number and percentage of subjects in the respective treatment arm that do not experience an endpoint event and that are censored before the SED, as well as reasons for censoring.

#### **4.3 Pharmacodynamic Endpoint(s)**

Not applicable.

#### **4.3.1.1 Pharmacokinetics**

Not applicable.

### **4.4 Immunogenicity**

Not applicable.

### **4.5 Safety Analyses**

The domain safety covers adverse events, clinical laboratory, vital signs, and ECG.

Tables and listings are, as a rule, provided for the SS, except for an SAE listing that displays SAEs for non-randomised subjects that occur during screening.

The primary method for presentation of summary of safety will be “during the study” (see Section 3.3.1.4 for the definition of this time period), reflecting the ITT approach used for the efficacy analyses. However, a selection of tabulations will be replicated for “on treatment” period, as supportive information.

#### **4.5.1 Adverse Events**

Occurrence of AEs during the course of the study will be summarized descriptively, using frequencies and percentages.

##### **4.5.1.1 Definitions and Derivations**

Adverse events will be coded using the latest version of MedDRA implemented at the time of database lock. The MedDRA version will be stated in a footnote in the relevant outputs.

**Oedema-related** events are defined as AEs with the following PT terms: Fluid overload, Fluid retention, Generalised oedema, Hypervolemia, Localised oedema, Oedema, Oedema Peripheral, Peripheral swelling.

**Pre-dialysis hypokalemia** (S-K < 3.0 mmol/L based on local laboratory assessment) will be reported as an AE regardless of whether there are associated signs and symptoms, and is indicated directly by the investigator in the appropriate eCRF form (note that hypokalemia could also be determined based on the central lab potassium evaluation, and would then be reported separately, see Section 4.6.2.1).

**Pre-dialysis hyperkalemia requiring rescue** is collected as an adverse event, and is indicated directly by the investigator in the appropriate eCRF form.

**Dialysis adequacy (Kt/V)** will be collected in eCRF only in Indian sites during visit 1 (screening), visit 4 (randomization) and thereafter during subsequent protocol specified onsite visits until the end of study intervention visit (EOIV) or premature study intervention discontinuation visit (PIDV).

**Duration variables** to be presented, where applicable (e.g. key subject information tables), are defined as follows:

- Time from planned treatment start date to onset of AE (days)
- Time from planned treatment start date to death (days)
- Time from planned treatment start date to AE becoming serious (days)
- Time from planned treatment start date to discontinuation of IP (days)
- Time from actual last dose date to death (days)
- Time from actual last dose date to AE start date (days)

The derivations for these variables will be the difference between the two dates stated above + 1 day.

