## 2 INTRODUCTION

Sodium zirconium cyclosilicate, hereafter abbreviated as SZC, is an oral, non-polymer inorganic cation-exchanger that represents a novel therapy for the treatment of hyperkalemia. SZC selectively captures potassium ions in exchange for hydrogen and sodium ions in the gastrointestinal tract, thereby reducing S-K concentration and removing potassium from the body through increased fecal excretion. SZC exerts its effect locally and it is not absorbed systemically.

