## **2.3      Benefit/Risk Assessment**

The primary benefit for participants randomized to SZC treatment is expected to be the maintenance of normokalemia during the LIDI, in line with what was observed in the DIALIZE study. Further, should the study hypothesis prove true, this may bring a consequent improvement in arrhythmia-related CV outcomes and urgent ED/hospital visits for hyperkalemia-related arrhythmias. The likelihood of treatment with SZC raising safety concerns is deemed to be low, as no clinically relevant safety findings were observed in the DIALIZE study.

Participants treated with placebo may not obtain any benefit in terms of hyperkalemia correction and maintenance but may benefit from the closer follow-up. Participants will receive alternative therapies whenever clinically indicated.

An established dose adjustment algorithm will be used during the study to titrate SZC doses to enable participants to achieve and maintain pre-dialysis normokalemia (S-K between 4.0 to 5.0 mmol/L) after the LIDI ([Section 6.1.2](#)). In accordance with the algorithm, the dose may be

increased, reduced, or kept unchanged, depending on the current potassium concentration, adapting the dosing regimen to each participant and preventing unnecessarily high exposure to the product.

The risks identified with SZC treatment include hypokalemia and edema-related events (includes fluid overload, fluid retention, generalized edema, hypervolemia, localized edema, edema, peripheral edema, peripheral swelling). In this study, the risk for hypokalemia is mitigated by periodic monitoring of potassium and adjustment of the SZC dose as necessary. Edema can be managed by conservative measures in line with standard clinical practice. No additional safety risks were identified in the DIALIZE study.

In conclusion, the favorable benefit-risk ratio that has been established for SZC in the clinical development program remains positive when SZC is used to treat hyperkalemia in participants on chronic hemodialysis, as shown in the DIALIZE study.

More detailed information about the known and expected benefits and potential risks of SZC may be found in the Investigator's Brochure.

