### **Events of special interest: oedema, hypokalemia and hyperkalemia**

An overview of oedema-related AEs, with number and percentage of subjects with an event with a particular PT term, will be presented.

Number of subjects with AE classified as hypokalemia, or hyperkalemia requiring rescue, will be tabulated in a similar manner.

Both of these overviews, oedema-related AEs and hypo-hyperkalemia AEs, will be replicated for the on-treatment period as well as during study.

**Dialysis adequacy (Kt/V)** as a continuous variable will be summarized descriptively as described in Section 3.3.

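### The oedema risk is defined by eight closed preferred terms and tabulated only term by term, so no pre-specified comparison by arm groups serious fluid-overload presentations

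*SAP*

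**What the plan says.** Protocol 2.3 states: "The risks identified with SZC treatment include hypokalemia and edema-related events". It explains the second risk in a parenthesis that "includes fluid overload, fluid retention, generalized edema, hypervolemia, localized edema, edema, peripheral edema, peripheral swelling".

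SAP 4.5.1.1 turns this into a programmable definition: oedema-related "events are defined as AEs with the following PT terms: Fluid overload, Fluid retention, Generalised oedema, Hypervolemia, Localised oedema, Oedema, Oedema Peripheral, Peripheral swelling".

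SAP 4.5.1.2 gives the group special status under the heading "Events of special interest: oedema, hypokalemia and hyperkalemia". The planned output is this: "An overview of oedema-related AEs, with number and percentage of subjects with an event with a particular PT term, will be presented". It is produced for the during-study and on-treatment periods.

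On mechanism, Protocol section 2 says: "SZC selectively captures potassium ions in exchange for hydrogen and sodium ions in the gastrointestinal tract". Participants receive hemodialysis three times a week (Protocol 5.1), and average treatment is expected to last about 37 months (Protocol 9.2).

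**The concern.** SZC exchanges potassium partly for sodium, and these participants rely on dialysis to remove fluid. It is clinically plausible that sodium and fluid retention would sometimes be recorded as its consequence: pulmonary oedema, pulmonary congestion or cardiac failure. Protocol 8.3.4 prefers a diagnosis to a list of signs and symptoms, which makes such recording more likely. An AE coded to one of those PTs alone cannot enter the special-interest oedema table.

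At stake is how readily an imbalance between arms in an identified risk can be seen. If related presentations sit on separate lines, no single line need look unusual. A grouping built after unblinding could be challenged as selective, whichever way it pointed. One fixed beforehand could not.

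**Working it through.** No sample-size, power or alpha figure is involved. The check compares the two lists and then traces where an unlisted term would be reported.

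**Step 1: compare the lists.** Protocol 2.3 has 8 terms and SAP 4.5.1.1 has 8: "Fluid overload, Fluid retention, Generalised oedema, Hypervolemia, Localised oedema, Oedema, Oedema Peripheral, Peripheral swelling". Spelling and word order aside, 8 of 8 match. The only difference is the introduction: the protocol's can be read as open, while the SAP's ("events are defined as AEs with the following PT terms") is closed.

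**Step 2: look for the omitted terms.** Pulmonary oedema, pulmonary congestion and cardiac failure terms: 0 in the protocol list, 0 in the SAP list.

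**Step 3: trace an AE coded to one of those PTs.**

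| Planned output | What it shows | Grouped comparison by arm? |
|---|---|---|
| AE overview (SAP 4.5.1.2) | Rows for hypokalaemia and for hyperkalemia requiring rescue; none for oedema | No |
| SOC/PT tables (SAP 4.5.1.2) | AEs, SAEs, AEs leading to discontinuation, and deaths; each PT on its own line | No, separate PTs |
| Most common AEs (SAP 4.5.1.2) | Only PTs in more than 10% of participants, arms combined | No |
| Special-interest oedema table (SAP 4.5.1.2) | The eight PTs, one by one; no pooled row and no serious-event split stated | No, and the AE is not included |
| Key subject information (SAP 4.5.1.2) | All SAEs, fatal AEs and AEs leading to discontinuation, by subject | No |
| Interdialytic weight gain (SAP 4.5.3.2) | A continuous measure at scheduled visits | No, it does not record clinical events |

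The weight measure has further limits as a substitute. By-visit summaries exclude unscheduled data (SAP 3.4.3), and weights are not collected at telephone or video visits (Protocol Table 2, footnote g).

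**Step 4: can a reader build the group from the tables?** Not exactly. A participant with two relevant PTs is counted on two lines, so adding PT counts overstates the number of participants with any event. This also applies to the eight listed terms, because no pooled row is stated for them.

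**The case against.** The strongest case against is that the plan is coherent and hides nothing. Three stronger readings are tempting, and the documents do not support them.

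- *A reader might infer that the SAP narrowed a wider protocol risk.* It did not. Protocol 2.3 gives the same eight terms, and a PT list has to be closed to be programmed. The two documents do not conflict.
- *A reader might infer that the table counts mainly mild events.* Fluid overload, Hypervolemia, Fluid retention and Generalised oedema are all listed, and neither document restricts them by severity or seriousness. An admission could be recorded as fluid overload, and a participant with both a listed and an unlisted PT is still counted.
- *A reader might infer that serious cases go unreported.* They appear in the SOC/PT tables by arm and, if serious, fatal or leading to discontinuation, in the key subject information. The DMC also reviews unblinded data for harm (Protocol 4.1 and Appendix A 5.4).

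It is also fair to say that neither document names pulmonary oedema or cardiac failure as a form of the SZC risk. Safety reporting is descriptive (Protocol 9.4.3), so no decision rule depends on the grouping.

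A broader group can also blur a signal. Take assumed figures, not estimates: listed terms in 5% of placebo and 6.5% of SZC participants, and non-overlapping unlisted terms in 5% of placebo participants.

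- No excess in the unlisted terms: 5 + 5 = 10% against 6.5 + 5 = 11.5%. The difference stays at 1.5 points, and the ratio falls from 6.5/5 = 1.30 to 11.5/10 = 1.15.
- The same relative excess: 10% against 6.5 + 6.5 = 13%. The difference doubles to 3 points, and the ratio stays at 1.30.

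All of this stands. It argues against replacing the eight-term list. It does not argue against a supplementary group shown beside it, and none of the existing outputs provides the missing grouped comparison.

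**Conclusion.** The point holds as a gap in pre-specified presentation. Both documents describe the edema risk with the same eight terms, the SAP closes the list, and the planned table counts PTs singly. Serious fluid-overload presentations coded to other PTs are reported but never compared between arms as a group. Hypokalaemia, the other risk named in Protocol 2.3, has its own row in the AE overview; oedema has none.

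The practical weight of this rests on one assumption that the documents do not state: that some pulmonary oedema, pulmonary congestion or cardiac failure events in this population arise from SZC's sodium and fluid effect. That is plausible, but the documents give no AE rates, so neither the share of events outside the list nor any loss of sensitivity can be estimated. No primary or secondary endpoint, significance level or estimand is affected. This is an inexpensive improvement to safety reporting and does not correct an error of analysis.

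**What to change.** Keep the eight-term definition, for consistency with Protocol 2.3. Before unblinding:

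1. In SAP 4.5.1.1, add one supplementary broad fluid-overload group: the eight terms plus Pulmonary oedema, Acute pulmonary oedema, Pulmonary congestion, Cardiac failure, Cardiac failure acute and Cardiac failure congestive (8 + 6 = 14 PTs). Check the names against the MedDRA version used at database lock.
2. In SAP 4.5.1.2, show a pooled any-event row by arm for both the narrow and the broad group, for AEs and for SAEs, during study and on treatment. Count each participant once per row.

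The cost is SAP wording and some programming on AEs that are already coded. No new data or study procedure is needed. The downside is lower specificity: cardiac failure has other causes and could dilute a signal. Showing the two groups side by side limits this, because a reader can see whether an imbalance lies in the listed terms, the added terms or both.
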